1.2 Name and Description of Investigational Product or Intervention

Study intervention: Oral furosemide

The information provided in this section was obtained from Food and Drug Administration (FDA) package insert.¹⁹ Furosemide (Lasix[®]) is a diuretic which is an anthranilic acid derivative. Tablets contain furosemide (active ingredient) and lactose monohydrate NF, magnesium stearate NF, starch NF, talc USP, and colloidal silicon dioxide SF (inactive ingredients). Chemically, it is a 4-chloro-N-furfuryI-5-sulfamoylanthranilic acid. It is available in 20, 40 and 80 mg tablets.

Furosemide is a white to off-white odorless crystalline power. It is practically insoluble in water, sparingly soluble in alcohol, freely soluble in dilute alkali solutions and insoluble in dilute acids.

Mechanism of action: Furosemide inhibits the absorption of sodium and chloride not only in the proximal and distal tubules but also in the loop of Henle. The action on the distal tubule is independent of any inhibitory effect on carbonic anhydrase and aldosterone.

Pharmacokinetics: The onset of diuresis following oral administration is within 1 hour. The peak effect occurs within the first or second hour. The duration of diuretic effect is 6 to 8 hours. In fasted normal men, the mean bioavailability of oral furosemide tablets is 64% of that from an intravenous injection of the drug. The terminal half-life of furosemide is approximately 2 hours. Peak plasma concentrations increase with increasing dose, but times-to-peak do not differ among doses. Furosemide is predominantly excreted unchanged in the urine.

Indications and usage: Furosemide is indicated in adults and pediatric patients for the treatment of edema associated with congestive heart failure, cirrhosis of the liver, and kidney disease. Oral furosemide may also be used in adults for the treatment of hypertension alone or in combination with other antihypertensive agents.

Contraindications: Furosemide is contraindicated in patients with anuria and in patients with a history of hypersensitivity to furosemide.

Dosing and dose changes with rationale

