1.3 Clinical Data to Date

Heart Failure: Most patients with heart failure and volume overload are initially treated with the combination of an oral loop diuretic (e.g. furosemide) and a low sodium diet. The diuretic response to furosemide is described by a threshold type dose-response curve linking the rate of diuretic excretion in the urine and the degree of natriuresis. There is virtually no increase in natriuresis until the threshold concentration of luminal diuretic is reached and, once the threshold is exceeded, the degree of natriuresis increases until a maximal ceiling is reached.^{22, 23} As the threshold concentration differs across patients, it is necessary to determine an effective dose in individual patients. The usual starting dose in furosemide-naïve patients without kidney dysfunction is furosemide 20 to 40 mg once or twice daily, and subsequent dosing is determined by the diuretic response. It is customary to double the prior dose when titrating furosemide for a diuretic response.²⁰ For patients with normal glomerular filtration rate, maximal single oral doses of furosemide are 40 to 80 mg. For patients with kidney insufficiency (impaired glomerular filtration rate), a higher maximum dose of 160 to 200 mg of furosemide can be given (maximum total daily dose of 600 mg).¹⁹ Dosing in patients who have received prior loop diuretic therapy is based upon the response to prior dosing amounts.²⁰

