2.1 Primary Objectives

Period 1 (dose escalation = short-term outcomes; 6-weeks) and Period 2 (follow-up = longer-term outcomes; 12-weeks)

Short-term and longer-term efficacy: To test the hypothesis that furosemide will increase 24-hour urine volume at its maximally tolerated dose in individuals with HD-dependent ESKD. 24-hour urine volumes will be used as the primary endpoint for both short-term and longer-term efficacy assessments.

Short-term and longer-term safety: To evaluate the short-term (6-weeks) and longer-term (12-weeks) safety of escalating doses of furosemide in individuals with HD-dependent ESKD. Safety outcomes will include the following:

- Serum potassium level <3.2 mEq/L
- Serum magnesium level <0.8 mg/dL
- Serum corrected calcium level <7 mg/dL
- Serum furosemide level >12 microgram/L
- Serious dialysis-associated hypotension defined as hypotension requiring hospitalization or treatment in an emergency room and not attributable to overt sepsis, acute myocardial infarction, or other cardiovascular event (e.g. aortic dissection)
- Severe or very severe rash, tinnitus, or hearing change not attributable to causes other than furosemide
- Inner EAR score decrease by ≥10 points

Short-term and longer-term tolerability: To evaluate the short-term and longer-term tolerability of furosemide in individuals with HD-dependent ESKD. Tolerability will be assessed by:

• Severe or very severe cramping, dizziness/pre-syncope, unusual tiredness/weakness, chest pain, nausea, vomiting, or diarrhea not attributable to causes other than furosemide

Short-term and longer-term acceptability: To evaluate the short-term and longer-term acceptability of furosemide in individuals with HD-dependent ESKD. Acceptability will be assessed by:

- Participant affirmative response to question: "If recommended, would you be willing to stay on the dose of furosemide you have received during the last week?"
- Recruitment rates
- Drop-out rates

Short-term adherence: To evaluate short-term and longer-term adherence to furosemide among individuals with HDdependent ESKD. Adherence will be assessed by:

- Pill counts
- Serum and urine furosemide levels

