4.4 Follow- up procedures (by visit types)

All study visits will occur at the time of routinely scheduled HD treatments at the patient's usual outpatient dialysis clinic. *Section 5* describes the measurements and assessments in detail.

Blood samples (weeks 1, 2, 3, 4, 5, 6, 10, 14, and 18): Blood will be obtained for the measurement of serum sodium, potassium, chloride, urea, creatinine, magnesium, calcium, albumin, and furosemide level. An additional 2.5 mL blood sample will be drawn, frozen, and stored in UNC Kidney Center -80° freezers for future testing as needed.

Urine samples (weeks -1, 5, 12, and 18): 24-hour urine collections will be obtained for the measurement of urine volume, sodium, urea, creatinine, and furosemide level. An aliquot of urine will be taken from the sample after the before-listed measurements are performed and be frozen and stored in UNC Kidney Center -80° freezers for future testing as needed.

Adherence assessments (weeks 1, 2, 3, 4, 5, 6, 8, 10, 12, 14, 16, and 18): Study staff will complete pill counts.

Acceptance assessments (weeks 1, 2, 3, 4, 5, 6, 8, 10, 12, 14, 16, and 18): Study staff will ask the participant the acceptance question.

Symptom assessments (weeks 1, 2, 3, 4, 5, 6, 8, 10, 12, 14, 16, and 18): Study staff will administer surveys evaluating patient-reported cramping, dizziness/pre-syncope, unusual tiredness/weakness, chest pain, rash, nausea, vomiting, diarrhea, tinnitus, hearing change, and numbness/tingling.

Hearing assessments (weeks 2, 4, 6, 10, 14, and 18): Study staff will administer the Inner EAR instrument.

Clinical data (weeks -4 to 18): HD treatment-level data (BPs, weights, dialysis prescription) will be obtained from the EHR.

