6.1 Primary Endpoints

Short-term and longer-term efficacy- urine volume (assessed separately)

- Among participants with baseline 24-hour urine volume ≥200 mL: incidence of ≥25% increase in urine volume
- Among participants with baseline 24-hour urine volume <200 mL: incidence of a ≥50 mL increase in urine volume to a urine volume of at least 100 mL/24-hours

Short-term and longer-term safety- electrolytes (assessed separately)

- Incidence of serum potassium <3.2 mEq/L
- Incidence of serum magnesium <0.8 mg/dL
- Incidence of serum corrected calcium <7.0 mg/dL

Short-term and longer-term safety- furosemide levels

• Incidence of serum furosemide level >12 microgram/L

Short-term and longer-term safety- BP

 Incidence of dialysis-associated hypotension requiring hospitalization or treatment in an emergency room and not attributable to overt sepsis, acute myocardial infarction, or other cardiovascular event (e.g. aortic dissection)²¹

Short-term and longer-term safety- symptoms (assessed separately)

- Incidence of severe or very severe patient-reported rash, tinnitus, or hearing change) not attributable to causes
 other than furosemide
- Incidence of 10-point decrease in Inner EAR instrument score

Short-term and longer-term tolerability- symptoms (assessed separately)

• Incidence of severe or very severe patient-reported cramping, dizziness/pre-syncope, unusual tiredness/weakness, chest pain, nausea, vomiting, or diarrhea not attributable to causes other than furosemide

Short-term and longer-term acceptability

• Incidence of an affirmative response to the furosemide acceptance question

Short term- and longer-term adherence

• Incidence of participants having <20% of furosemide pills remaining at pill counts

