6.2 Exploratory Endpoints

Short-term and longer-term efficacy- alternative definitions (assessed separately)

- Absolute change in urine volume from baseline (continuous in mL urine)
- Percentage change in urine volume from baseline (continuous in %)

Short-term and longer-term safety- electrolytes- alternative definitions (assessed separately)

- Absolute change in serum potassium from baseline (continuous in mEq/L)
- Absolute change in serum magnesium from baseline (continuous in mg/dL)
- Absolute change in serum corrected calcium from baseline (continuous in mg/dL)
- Percentage change in serum potassium from baseline (continuous in %)
- Percentage change in serum magnesium from baseline (continuous in %)
- Percentage change in serum corrected calcium from baseline (continuous in %)

Short-term and longer-term safety- BP- alternative definitions (assessed separately)

- Incidence of intradialytic systolic BP <80 mmHg²¹
- Incidence of intradialytic systolic BP <90 mmHg⁴¹
- Lowest systolic BP during HD (continuous in mmHg)

Short-term and longer-term acceptability alternative definitions (assessed separately)

- Number (percentage) of participants withdrawing from the study
- Number (percentage) period 1 participants not continuing to period 2

Short-term and longer-term adherence alternative definitions (assessed separately)

- Number (percentage) of furosemide tablets not taken (# tablets remaining/# tablets provided)
- Serum furosemide level (continuous in microgram/L and binary, present vs. absent)
- Urine furosemide level (continuous in microgram/L and binary, present vs. absent)

Clinical endpoints (assessed separately)

- Change in 24-hour creatinine clearance from baseline (continuous in ml/min/1.73m²)
- Percentage change in 24-hour creatinine clearance from baseline (continuous in %)
- Change in 24-hour fractional excretion of sodium from baseline (continuous in %)

- Change in 24-hour fractional excretion of urea from baseline (continuous in %)
- Percentage change in 24-hour fractional excretion of urea from baseline (continuous in %)
- Pre-HD systolic BP (mmHg on a per-HD treatment basis)
- IDWG (kg on a per-HD treatment basis)
- UF volume (mL on a per-HD treatment basis)
- UF rate (mL/h/kg on a per-HD treatment basis)
- Target weight achievement (post-HD weight (kg) within 1kg of prescribed target weight) (binary on a per-HD treatment basis)

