Retention of research participants in clinical trials is always a concern. However, the activities of the proposed study are not especially burdensome. Participants will be taking a twice a day medication that is unlikely to have substantial side effects. The duration of the entire study is relatively short (18 weeks). The dose escalation period, the first 6 weeks of the study, requires blood draws at weekly intervals during participants' routine HD treatments and two urine collections. Clinic personnel will collect blood samples via the vascular access at the start of dialysis treatment. Therefore, study blood collections will not necessitate additional needle sticks. Participants will return urine collection containers to the study team at routine HD treatments. In the subsequent 12-week follow-up period, blood draws occur every 4 weeks during participants' routine HD treatments and urine will be collected twice. All study visits will occur at the time of regularly scheduled dialysis treatments at the participant's dialysis clinic. Participants will receive up to \$199 remuneration for study participation. We will encourage adherence to study testing by 1) timing remuneration provision with urine sample collections and 2) providing larger remuneration amounts to participants who return their 24-hour urine collection samples to the study team compared to participants who do not return their 24-hour urine samples. The research team will remain in close contact with participants through weekly study visits in the first 6 weeks of the study and then every other week visits in the final 12 weeks of the study. In addition, the research team will provide participants with the research team's contact information (telephone and email) and encourage participants to contact the team at any time. The research team will provide participants with updates on study progress at pre-specified time points. At the conclusion of the study, results will be shared with participants who expressed interest in receiving them via follow-up letters written at a 5th grade reading level.

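### The continuous urine furosemide adherence measure is a concentration that depends on the efficacy outcome and is not scaled to dose, and the serum level is not timed to the last dose

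*Combined protocol and SAP*

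**What the plan says.** Section 2.1 lists "Serum and urine furosemide levels" beside pill counts as the ways in which adherence will be assessed. Section 6.1 makes the pill count the primary adherence endpoint, with fewer than 20% of pills remaining as the criterion. Section 6.2 places the drug levels among the exploratory alternatives: "Serum furosemide level (continuous in microgram/L and binary, present vs. absent") and "Urine furosemide level (continuous in microgram/L and binary, present vs. absent"). Section 6.3.5 lists the same levels under acceptability, not adherence, and says that the exploratory measures will not be assessed by p-values.

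On how the samples arise, Section 4.4 states: "24-hour urine collections will be obtained for the measurement of urine volume, sodium, urea, creatinine, and furosemide level". Volume and drug level therefore come from the same container, at weeks -1, 5, 12 and 18. Section 4.1 places blood draws at mid-week dialysis visits, and Section 9.1 adds: "Clinic personnel will collect blood samples via the vascular access at the start of dialysis treatment".

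On pharmacology, Section 1.2 states: "The terminal half-life of furosemide is approximately 2 hours". Section 1.3 describes a dose-response curve "linking the rate of diuretic excretion in the urine and the degree of natriuresis".

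Nowhere do the documents specify an amount of furosemide excreted per 24 hours, a scaling of the level to the prescribed dose, or a record of the time from last dose to blood draw.

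**The concern.** A concentration is an amount divided by a volume. Here the volume is the quantity that the drug is meant to change, and a rise in it defines efficacy: for baseline volumes of 200 mL or more, the primary endpoint is the "incidence of ≥25% increase in urine volume". The continuous urine marker of adherence is therefore tied arithmetically to the efficacy outcome. It also mixes dilution with prescribed dose. Participants may be on different steps of the escalation scheme, and those who entered on a loop diuretic follow individual doses.

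The serum marker has a different weakness. With a short half-life and a draw fixed to the dialysis session, not to the dose, it mainly shows whether the latest dose was taken and how long ago.

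At stake is whether the drug levels can corroborate the pill counts and help to separate non-response from non-adherence. That matters for a pilot whose stated purpose includes providing a basis for a later randomized trial. Section 3.5.11 anticipates that some containers will not be returned, and the levels are the only other adherence assessment that Section 2.1 names.

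**Working it through.** The plan gives no figure for these measures, so there is nothing to reproduce. The check is direct arithmetic.

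**Inputs from the documents:** responder volume ratio of 1.25, or an absolute rise of at least 50 mL to at least 100 mL when baseline is below 200 mL (6.1); pill-count criterion of under 20% remaining (6.1); twice-daily dosing at 80, 120 or 160 mg per dose for participants not on furosemide at entry, and 50% steps for prior loop-diuretic users (3.5.2); half-life of about 2 hours (1.2).

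**Assumptions:** 12-hour dosing interval; first-order elimination; half-lives of 4 to 10 hours as a range, because the documents give no value for hemodialysis patients; 10 mg/24 h as an illustrative excreted amount.

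**1. Urine, effect of volume.** Concentration ratio = amount ratio / volume ratio. At equal amount:

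- volume x1.25: 1/1.25 = 0.80, a 20% fall
- volume x1.5: 1/1.5 = 0.67, a 33% fall
- volume x2 (for example 50 to 100 mL): 1/2 = 0.50, a 50% fall

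The 0.80 is also the reading of someone who took 80% of the pills with no change in volume, if excretion is proportional to intake. That is the boundary of the pill-count criterion.

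Between participants, 10 mg in 200 mL reads 10,000/0.2 = 50,000 microgram/L, and the same 10 mg in 1,000 mL reads 10,000 microgram/L.

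**2. Urine, when the amount also changes.**

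- amount x1.25, volume x1.25: ratio 1.00
- amount x1.5, volume x1.25: ratio 1.20
- amount x2.25 (two compounded 50% steps, 1.5 x 1.5), volume x1.25: ratio 1.80

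The sign of the distortion is therefore not fixed.

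**3. Urine, effect of dose.** 160 mg twice daily is 320 mg/day and 80 mg twice daily is 160 mg/day, and 320/160 = 2. At equal volume and equal fraction excreted, a participant on the higher dose who takes half the pills reads the same as a fully adherent participant on the lower dose.

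**4. Serum.** Let r = 2^(-12/half-life). At steady state the share of the level that comes from the last dose is 1 - r. The fall between 2 and 12 hours after a dose is 2^(10/half-life).

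| Half-life | r | Share from last dose | Fall, 2 to 12 h |
|---|---|---|---|
| 2 h (documents) | 0.0156 | 98.4% | 32-fold |
| 4 h (assumed) | 0.125 | 87.5% | 5.7-fold |
| 6 h (assumed) | 0.25 | 75% | 3.2-fold |
| 10 h (assumed) | 0.4353 | 56.5% | 2.0-fold |

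**5. After the change.** Excreted amount (mg/24 h) = concentration (microgram/L) x volume (L) / 1,000. In step 1 the amount ratio is 1.00 in every line, so the dilution artefact disappears. Dividing by the prescribed daily dose removes the two-fold dose difference in step 3, under the same proportionality.

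**The case against.** A reader might infer that the best responders will look least adherent. The documents do not support that. It requires equal excreted amounts in responders and non-responders, and Section 1.3 links response to the rate at which drug is excreted in urine, so responders may excrete more. Step 2 shows that the distortion can then vanish or reverse. What stands is that an adherent responder can look less adherent, and that the reader of the concentration cannot tell which case applies.

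Nor should the 20% and 50% be read as falls that the study would observe within most participants. Those not taking furosemide at entry have no drug in the week -1 collection, and their first on-drug collection, at week 5, follows scheduled escalation. They have no on-drug level from before the response. Those already on furosemide may have had dose steps before week 5. The problem is mainly one of comparing participants, and of comparing weeks 5, 12 and 18 if volume drifts. It is also not shown that differences between participants mostly reflect residual volume.

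The present/absent urine marker is largely immune to dilution, unless levels lie near an assay limit that the documents do not give. It can still corroborate pill counts.

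For serum, a reader might infer that the level reflects only the last dose. That fits the stated 2-hour half-life, but Section 1.2 takes its pharmacology from the package insert and gives no value for these patients; at longer half-lives the statement weakens to mainly. Draws are also repeated nine times on treatment, which helps. The blood-draw form is not in the documents, so the absence of dose times is an absence from the protocol text only.

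Excreted amount has faults of its own. It contains the efficacy volume as a factor, an incomplete collection lowers both, and it depends on absorption and residual function. This is a fair reason not to treat it as a pure adherence measure.

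Finally, nothing is lost irretrievably for urine, since volume and concentration are both kept. Sections 6.3.5 and 6.3.7 allow transformations and changed outcome definitions. That wording is generic, however: it names neither an excreted amount nor a dose scaling, and it cannot recover dose times that were never recorded.

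**Conclusion.** The concern holds for the continuous urine measure and, more mildly, for the serum level. The urine concentration mixes adherence, prescribed dose and the efficacy outcome. At equal excretion the distortion is 20% at the responder cut-off and 50% at a doubling of volume, with a direction that depends on how the excreted amount moves. The serum level mainly reflects recent dosing and sampling time: about 98% comes from the last dose at the stated half-life, and about 56 to 88% at assumed half-lives of 10 to 4 hours, given a 12-hour interval and first-order elimination.

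The consequence is limited. The levels are exploratory, no p-values attach to them, and the primary adherence endpoint is the pill count. A reader might take adherence being a primary objective to mean that a primary result is compromised; Section 6.1 shows that no primary adherence result uses these levels. The case for change rests on its low cost and on the value of an interpretable biochemical measure beside the pill count.

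**What to change.** In Sections 6.2 and 6.3.5, add furosemide excreted per 24 hours (concentration x 24-hour volume, mg/24 h) at weeks 5, 12 and 18, also as a fraction of the daily dose prescribed at the time of the collection. Use it, not raw concentration, as the continuous urine measure of adherence and exposure, and keep the present/absent measure alongside. State that it will be interpreted with collection completeness and residual function, to which it is sensitive.

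Record the clock times of the last furosemide dose and of each blood draw, and interpret serum levels by hours since dose. The same times would help with the serum furosemide safety endpoint in Section 6.1, which uses the same samples.

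Reconcile the label: the levels are adherence measures in Section 6.2 and acceptability measures in Section 6.3.5.

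The cost is one derived variable from data already collected, two recorded times per blood draw, and an edit to the text. The time of the last dose will be self-reported and so inexact.

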3.4 Study Population

Participant Inclusion Criteria

- Patient self-report of at least 1 cup urine/24-hours⁴²
- Age ≥18 years
- Receipt of thrice weekly in-center HD at a participating clinic (UNC-associated Carolina Dialysis- Carrboro, Siler City, Pittsboro, Sanford, and Lee County)
- ≥60 days receiving in-center HD
- Willingness to take study medication and undergo study testing
- Ability to provide informed consent

Participant Exclusion Criteria

- Known allergy to loop diuretic
- History of poor adherence to HD or medical regimen per nephrologist
- >1 hospitalization in prior 30-days
- Frequent hypotension (systolic BP <80 mmHg at >30% of HD treatments in prior 30-days)²¹
- Cirrhosis per nephrologist
- Hearing disorder per nephrologist
- Serum potassium <3.5 mEq/L, magnesium <1 mg/dL, or corrected calcium <8 mg/dL in prior 30-days
- Taking a non-loop diuretic (e.g. spironolactone, eplerenone, ethacrynic acid, thiazides)
- Taking an aminoglycoside, cisplatin, methotrexate, cyclosporine, ACTH, lithium, phenytoin, or oral/intravenous steroid
- Natural licorice consumption
- Prisoners, patients with significant mental illness
- Pregnant patients and nursing mothers

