4 STUDY PROCEDURES

4.1 Overview (Tables 2 and 3)

All study visits will occur at the participant's dialysis clinic at routinely scheduled HD treatments.

- There will be one study visit during the baseline period.
- Dose escalation period (period 1): Blood samples will be collected weekly at mid-week treatment visits (i.e. Wednesday or Thursday during weeks -1, 1, 2, 3, 4, 5 and 6) prior to scheduled dose initiation or dose titration. Urine samples will be collected twice during the dose escalation period at mid-week treatment visits (i.e. Wednesday or Thursday during weeks -1 and 5). Study drug visits will be conducted every two weeks at the first weekly treatment (i.e. Monday or Tuesday during weeks 0, 2, 4, and 6). This structure was selected so that blood results will be collected and analyzed the week prior to study drug dose titration. As such, test results will be available prior to potential dose titration. Adherence and symptom assessment visits will be conducted weekly at the first treatment of each week (i.e. Monday or Tuesday during weeks 1, 2, 3, 4, 5 and 6). Hearing

assessments will be conducted every two weeks at the first weekly treatment (i.e. Monday or Tuesday during weeks 2, 4, and 6).

- Follow-up period (period 2): Blood samples will be collected at mid-week treatment visits every 4 weeks (i.e. Wednesday or Thursday during weeks 9, 13 and 17). Study drug visits will be conducted at the first treatment of each of the subsequent weeks (i.e. Monday or Tuesday during weeks 10 and 14). As in the dose escalation period, this structure was selected so that blood results will be available prior to additional study drug administration. Study adherence and symptom assessment visits will be conducted every 2 weeks at the first weekly HD treatment in the scheduled week (i.e. Monday or Tuesday during weeks 8, 10, 12, 14, 16, and 18). Hearing assessments will be conducted every four weeks at the first weekly treatment (i.e. Monday or Tuesday during weeks 10, 14, and 18). Urine sample visits will be conducted at the mid-week treatments of the 12th week and final week of the follow-up period (i.e. Wednesday or Thursday during weeks 12 and 18). All remaining study drug will be returned at the first weekly treatment (i.e. Monday or Tuesday) of week 19. A final pill count (adherence assessment) will be performed upon study drug return (week 19).

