- Post-HD weight- target weight difference (post-HD weight prescribed dry/target weight, kg on a per-HD treatment basis)
- Extra HD treatments (number)
- Hospitalizations (number)

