Analogous to the primary analyses, percentage change measures, change measures, and value measures will be analyzed via one-way repeated measures of analysis of variance to determine the presence of absence of dose-related differences. In addition, we will use mixed effects modeling to test the effect of increased dose and duration with the fixed effect of time (dose), random subject effect, and an unstructured repeated covariance type. We will use generalized estimating equations to assess categorical outcomes. We will also consider binary outcomes as rates (events/time). Distribution of the exploratory parameters will be examined and appropriate transformation will be applied. These analyses are considered hypothesis-generating, and we will examine directionality and strength of relationships but will not assess via p-values.

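### IDWG and UF volume are analysed per dialysis treatment with no allowance for the interdialytic interval, so a change in extra or missed sessions from baseline moves both without any drug effect

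*Combined protocol and SAP*

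**What the plan says.** Participants follow a fixed schedule: section 3.4 requires "Receipt of thrice weekly in-center HD at a participating clinic". Section 4.1 places the first session of the week on Monday or Tuesday and the mid-week session on Wednesday or Thursday. A regular week therefore has intervals of 2, 2 and 3 days.

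The clinical endpoints in section 6.2 include "IDWG (kg on a per-HD treatment basis" and "UF volume (mL on a per-HD treatment basis". Neither is divided by the time since the previous treatment. The same list has "Extra HD treatments (number" as a separate outcome; missed sessions are not listed. Section 4.1 treats all dialysis sessions in the 18-week period as study treatments, with no rule for an extra session or for the session after a missed one. Table 2 has the session data start in week -4, so there is a baseline for comparison.

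For continuous exploratory endpoints, section 6.3.5 plans one-way repeated-measures ANOVA and "mixed effects modeling to test the effect of increased dose and duration with the fixed effect of time (dose"), with a random subject effect and unstructured covariance. No section names the interdialytic interval, weekday or session position as a covariate, stratum or divisor. Section 6.3.6 adjusts subgroup models for baseline factors only. Section 6.3.7 lists variations in covariates as a sensitivity analysis without saying which.

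**The concern.** Fluid gain builds up over the interval between treatments. A mean per treatment therefore depends on two things: gain per day, which the drug is meant to change, and the number of treatments sharing the week's gain. The planned models cannot tell these apart.

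Section 3.2 gives every participant furosemide, so no concurrent group shows how session frequency would have moved by itself. Session frequency may also respond to treatment, since extra sessions are an outcome. If furosemide reduced them, per-treatment IDWG would rise mechanically and hide some of the benefit; more extra sessions on treatment would look like benefit.

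The background in section 1.1 rests largely on weight gain and ultrafiltration. Section 6.3.1 puts the weight on point and interval estimates, and section 6.3.5 will read direction and strength. A shift in the point estimate is what would mislead such a reading.

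**Working it through.** **The plan's own figure.** None exists for IDWG or UF volume. The only power calculation (section 6.4) concerns urine volume and is not affected.

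**Inputs from the plan.** Three sessions a week; 2-week dose steps and a 12-week period 2; 36 participants.

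**Assumed inputs, not in the plan.** Constant daily gain, set at 1.0 kg/day where kilograms are needed. UF volume is taken to follow the weight gained, so its relative shift is the same.

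**Step 1: one participant.** Mean IDWG per treatment = daily gain × days ÷ number of treatments. At constant daily gain the relative change is (scheduled treatments ÷ actual treatments) − 1.

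| Span | Scheduled | One extra session | One missed session |
|---|---|---|---|
| 1 week | 3 | 3/4 − 1 = −25% | 3/2 − 1 = +50% |
| 2-week dose step | 6 | 6/7 − 1 = −14% | 6/5 − 1 = +20% |
| 12 weeks | 36 | 36/37 − 1 = −2.7% | 36/35 − 1 = +2.9% |

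**Step 2: the group mean at 1.0 kg/day.** With full attendance, mean IDWG is 7/3 = 2.333 kg.
- Extra session in 10% of on-treatment weeks, none at baseline: 7/3.1 − 7/3 = 2.258 − 2.333 = −0.075 kg.
- Missed session in 10% of on-treatment weeks, none at baseline: 7/2.9 − 7/3 = 2.414 − 2.333 = +0.080 kg.
- At 5% of weeks the shifts are 7/3.05 − 7/3 = −0.038 kg and 7/2.95 − 7/3 = +0.040 kg.

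**Step 3: simulation with no drug effect.** With 36 participants, 4 baseline and 18 study weeks, and a random-intercept model on sessions, the 10% scenarios gave −0.082 kg (extra) and +0.088 kg (missed). Participant-period means gave about −0.07 and +0.08 kg. The error was about zero when days since the previous treatment entered the model (−0.004 and +0.004 kg) or when gain was expressed per day.

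**Step 4: scale.** If intake is unchanged, 100 mL/day more urine lowers IDWG by 0.1 × 7/3 = 0.23 kg per treatment. A shift of 0.07 to 0.09 kg is about a third of that. To mimic it fully at 1.0 kg/day, extra sessions would be needed in 3/(1 − 0.1) − 3 = 0.33, or one third, of on-treatment weeks.

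**The case against.** The bias needs session frequency to differ between baseline and treatment, and the plan gives no rates. Extra and missed sessions pull in opposite directions. Section 3.4 excludes patients with poor dialysis adherence or more than one hospitalization in the prior 30 days. The largest percentages belong to one participant in one week; over 12 weeks they fall below 3%. The primary efficacy endpoint is urine volume, and IDWG and UF volume are hypothesis-generating. All of this stands, and it limits the point to a minor one. It does not remove the point: the entry criteria do not prevent extra sessions, and nothing in the plan would show whether a shift had occurred.

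A second objection concerns the remedy. Treatment may change how often extra sessions occur, so the interval is a post-treatment variable, and conditioning on it changes the question. Per-treatment IDWG is also a legitimate endpoint. This stands as well, and it is why the adjusted model belongs among the sensitivity analyses under its own label.

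A reader might also infer that the 2-2-3 pattern, left in the residual, makes the confidence intervals too wide. The plan does not support that. Over whole weeks every participant-period mean contains the same pattern, so it cancels in the change from baseline. In simulation (assumed gain 1.0 kg/day, residual SD 0.6 kg), participant-period means gave an SE of 0.033 kg with or without the adjustment. An inflated SE arises only if sessions are treated as independent within a participant, which section 6.3.5 does not state. When response was also allowed to vary between participants (assumed SD 0.3 kg), adding the interval to a random-intercept model brought its SE down to 0.034 kg, against a true sampling error of about 0.06 kg. That is too small.

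**Conclusion.** The point holds as a conditional bias in two exploratory endpoints. Per-treatment IDWG and UF volume confound gain per day with session frequency, and a single-arm comparison with baseline cannot separate them. The size is roughly 0.07 to 0.09 kg if an extra or a missed session occurs in 10% of on-treatment weeks and not at baseline, and about half that at 5%. It is zero with full attendance, or when session frequency is the same in both periods. The percentages need only constant daily gain; the kilogram figures also need the assumed 1 kg/day and scale with it. The figure for UF volume assumes that removal follows gain.

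It would be tempting to extend this to pre-dialysis blood pressure, UF rate and the difference between post-dialysis and target weight. The documents give no relation between these and the interval, so no shift can be stated for them.

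**What to change.** - **Section 6.2:** add IDWG and UF volume per interdialytic day, each defined as the participant's total over the period divided by the total days since the previous treatment, and report them beside the per-treatment values.
- **Section 6.3.5 (with 6.3.7):** for these two endpoints only, add a sensitivity model with days since the previous treatment as a fixed effect. Label the result a gap-adjusted effect, because treatment may itself change the number of extra sessions.

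The interval comes from the session dates that belong to the treatment-level extraction already planned in section 4.4, so no visit, sample or participant is added. The cost is a few lines of analysis code, one extra reported quantity and a second estimand to explain. The per-treatment endpoints stay as they are.
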